9. QUALITY CONTROL AND QUALITY ASSURANCE OF THE STUDY

Data collection will be verified by at least two individuals, and statistical analyses will be performed by professional statisticians. The writing and revisions of the manuscript will undergo thorough discussion and modification within the department.

10. DATA SAFETY MONITORING

The clinical study will establish a corresponding data safety monitoring plan based on the level of risk involved. All adverse events will be documented in detail, appropriately handled, and tracked until resolved or the patient's condition is stabilized. Serious adverse events and unexpected events will be promptly reported to the ethics committee, regulatory authorities, sponsors, and drug supervision departments as required. The principal investigator will conduct regular cumulative reviews of all adverse events and will convene investigator meetings to assess the risks and benefits of the study when necessary. Studies with risks greater than minimum will arrange for independent data monitors to oversee the study data, and high-risk studies will establish an independent Data Safety Monitoring Board (DSMB) to review accumulated safety and efficacy data and make recommendations on whether the study should continue.

11. STATISTICAL PROCESSING

Intention-to-Treat (ITT) Population: Defined as all participants who entered the trial; the ITT population will serve as the primary analysis group for this study's efficacy evaluation.

Per-Protocol Set (PPS): The PPS is a subset of the ITT population, consisting of participants who were randomly assigned and underwent at least one treatment with tumor assessment and who had no significant protocol deviations that could materially affect primary efficacy evaluations. Analysis based on the PPS will serve as supportive analysis to complement the ITT-based analysis.

Safety Set (SS): Defined as all participants who received at least one dose of the investigational drug. The safety analysis population will be the primary analysis group for safety indicators and will be based on the treatment groups actually received.

Kaplan-Meier methods will be used to summarize Progression-Free Survival (PFS) and Overall Survival (OS); results will provide the median PFS and OS, along with 95% confidence intervals for all participants in the trial (ITT population). The Objective Response Rate (ORR) (defined as CR + PR) and Disease Control Rate (DCR)

(defined as CR + PR + SD) will be estimated with 95% credible intervals. Adverse event data for all participating patients will be summarized using descriptive statistics.

Patient data and outcome parameters will be entered into GraphPad Prism (version 9.1.2) and analyzed using the non-parametric Mann-Whitney U test (for continuous variables) to compare differences between two groups. For comparisons among more than two patient groups, the non-parametric Kruskal-Wallis test will be employed, followed by Dunn's post-hoc test with Bonferroni correction. Fisher's exact probability method will be used for between-group comparisons of categorical variables.

For all statistical analyses, a p-value of less than 0.05 will be considered statistically significant.

12. ETHIC OF CLINICAL RESEARCH

The clinical study will adhere to the relevant regulations set forth in the Declaration of Helsinki by the World Medical Association. Clinical research will commence only after the ethical review board approves the study protocol. The investigator is responsible for providing each participant or their representative with a complete and comprehensive introduction to the study's purpose, procedures, and potential risks before enrollment, and obtaining written informed consent. Participants will be informed of their right to withdraw from the study at any time, and the informed consent document will be retained as part of the clinical research records. The privacy and data confidentiality of participants will be protected throughout the research process.

13. RESEARCH SCHEDULE

August 2024 – July 2025: Patient enrollment, treatment, and data collection

August 2025 – December 2025: Follow-up and data organization/statistics

January 2026 – June 2026: Data analysis and manuscript writing

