Efficacy Analysis: The Objective Response Rate (ORR) will be calculated as the proportion of patients in the ITT population who achieved the best overall response of complete response (CR) or partial response (PR). The Disease Control Rate (DCR) will be calculated as the proportion of patients in the ITT population who achieved the best overall response of CR, PR, or stable disease (SD). For efficacy endpoints such as overall survival (OS) and progression-free survival (PFS), the Kaplan-Meier method will be used to estimate the median times and list the median events along with their two-sided 95% confidence intervals.

Patient data and outcome parameters will be inputted into GraphPad Prism (version 9.1.2) and analyzed using the non-parametric Mann-Whitney U test (for continuous variables) to compare differences between two groups. For comparisons among more than two patient groups, the non-parametric Kruskal-Wallis test will be applied, followed by Dunn's post-hoc test with Bonferroni correction. Fisher's exact test will be used for intergroup comparisons of categorical variables.

The serum protein abundance data from patients receiving Sintilimab + Ramucirumab + chemotherapy will be analyzed using the Cox proportional hazards model and Benjamini-Hochberg

	
multiple hypothesis correction ("R," version 4.2.1). A sample will be identified as an outlier using PCA plots and median vs. interquartile range (IQR) plots. This sample will be excluded from the phase one analysis. Samples with QC warning status will also be excluded from both analyses on a per-panel basis. The results will then be adjusted for multiple testing using the Benjamini-Hochberg method. Hazard ratio (HR) will be based on 1 NPX difference. The association between baseline NPX (v1) and ΔNPX (Δv2/v3-v1) plasma protein levels and PFS will be assessed by plotting Kaplan-Meier curves and calculating log-rank p-values. Patients receiving Sintilimab + Ramucirumab + chemotherapy will be evaluated by dividing them into low or high expression "risk groups" based on the median expression values of each parameter as a threshold. For all statistical analyses, a p-value of less than 0.05 will be considered statistically significant.

Research progress	August 2024 - July 2026

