1. BACKGROUND

Gastric cancer (GC) is a primary epithelial malignancy originating in the stomach and is one of the most common malignant tumors worldwide. In China, the incidence of gastric cancer ranks third, and its mortality rate also ranks third (1). There are approximately 1.2 million new cases of gastric cancer globally each year, with about 40% occurring in China (2). Even after radical surgery and adjuvant chemotherapy, the risks of local recurrence and distant metastasis remain high. For patients with unresectable locally advanced, recurrent, or metastatic gastric and gastroesophageal junction adenocarcinoma, the five-year survival rate is only about 13.9%. The incidence of liver metastasis in gastric cancer is higher than that of other organs. Once liver metastasis occurs, it typically indicates that most patients have lost the chance for radical treatment, and their long-term survival rate is extremely low. Although some cases can be managed with surgical interventions or other methods, systemic treatment remains the primary approach for patients with gastric cancer accompanied by liver metastasis. Historically, fluorouracil combined with platinum-based drugs has been the preferred treatment regimen for advanced gastric cancer. In recent years, the addition of immune checkpoint inhibitors has brought new hope for treating advanced gastric cancer with liver metastasis.

The emergence of immune checkpoint inhibitors (ICIs) targeting programmed cell death protein 1 (PD-1) and programmed death ligand 1 (PD-L1) has revolutionized cancer treatment, providing robust and durable responses in GC. Numerous clinical trials have confirmed the significant role of PD-1 monoclonal antibodies combined with chemotherapy as first-line treatment for advanced gastric cancer. For example, the CheckMate-649 study showed that in the Chinese subgroup with a CPS ≥ 5 , the combination of Nivolumab and chemotherapy had a better overall survival (OS) than chemotherapy alone (mOS 14.3 months vs. 10.2 months, HR 0.61 [0.44-0.85]); and also better progression-free survival (PFS) (mPFS 8.3 months vs. 5.6 months, HR 0.57 [0.40-0.80]) (3). The ORIENT-16 study demonstrated that in the CPS ≥ 5 population, the combination of Sintilimab and chemotherapy had superior OS compared to the

chemotherapy group (mOS 18.4 months vs. 12.9 months, HR 0.660 [0.505-0.864]); and better PFS (mPFS 7.7 months vs. 5.8 months, HR 0.628 [0.489-0.805]) (4).

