5.1. Sample Size Calculation

Based on a clinical study conducted by Yang et al. involving 60 patients with gastric cancer liver metastasis who received chemotherapy or immunotherapy combined with chemotherapy, the experimental group ($n = 30$) received continuous

intravenous infusion of Endu combined with the SOX regimen, while the control group (n = 30) received only the SOX regimen. The overall response rates (ORR) were 63.3% and 43.3%, respectively (PMID: 30539861). Considering that immunotherapy combined with anti-vascular treatment and chemotherapy provides a better response for gastric cancer with liver metastasis compared to chemotherapy alone, it is expected that the ORR for patients receiving this combined treatment will increase to 65%. Assuming the original ORR is 43%, under the conditions of a type I error of 0.05 and a power of 0.8, and considering a dropout rate of 20%, the study plans to enroll a total of 39 participants.

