6. OBSERVATIONAL ITEMS AND TESTING POINTS

Screening Period: Once patients are enrolled, blood tests (including complete blood count, coagulation function, tumor markers, myocardial markers, thyroid function, and microprotein expression levels) will be conducted one week before the start of the first treatment cycle, along with the collection of fecal samples, chest and abdominal imaging (plain scan or enhanced scan), and cardiac function evaluation (two-dimensional echocardiogram). Patients' age, gender, and other basic clinical data will be collected and organized. Gastric mucosal tissue specimens will be collected for intratumoral microbiome detection before the first treatment.

After Every 2 Treatment Cycles: After every 2 cycles of treatment with Sintilimab, Ramucirumab and chemotherapy, peripheral blood and fecal samples will be collected, and peripheral blood microprotein expression levels and gut microbiome analysis will be conducted during imaging assessments when the best overall efficacy is observed.

Disease Progression: If patients experience symptom deterioration or new symptoms, peripheral blood microprotein expression levels and fecal gut microbiome analyses will be performed within one week after confirming symptom deterioration or the emergence of new symptoms.

Follow-Up Period: During the treatment period, if the patient's disease does not progress, follow-ups are required every 3 months following the completion of 6 cycles of treatment, including: (1) routine follow-up assessments: clinical history, physical examination, routine hematological tests (complete blood count and chemical analysis, tumor markers CEA and CA199), Helicobacter pylori testing, nutritional evaluation (vitamin B12, iron), and enhanced CT scans of the chest, abdomen, and pelvis; (2) If patients experience symptom deterioration or new symptoms emerge, blood and fecal sample collections must be completed within one week, along with peripheral blood protein detection and gut microbiome analyses. Upon the patient's death, overall survival (OS) will be recorded, marking the clinical trial observation endpoint.

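### No OS data cut-off is stated. If it is the December 2025 end of follow-up in the schedule, the promised 95% CI for median OS will usually have no upper limit

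*Combined protocol and SAP*

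**What the plan says.** Enrolment runs from August 2024 to July 2025 (synopsis; sections 3.1 and 13). Section 13 then gives a single follow-up line, "August 2025 – December 2025: Follow-up and data organization/statistics", and assigns January to June 2026 to analysis and writing.

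Two other places do not fit a December 2025 close. Section 6 says that on a patient's death "overall survival (OS) will be recorded, marking the clinical trial observation endpoint", with no calendar limit. The synopsis row on research progress gives "August 2024 - July 2026".

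For the analysis, section 11 says that the "results will provide the median PFS and OS, along with 95% confidence intervals for all participants in the trial (ITT population"); the synopsis says much the same. No OS cut-off date, minimum follow-up, target number of deaths or expected median OS appears anywhere. The only OS medians are the background benchmarks in section 1. One trial, with sintilimab plus chemotherapy, is cited as "mOS 18.4 months vs. 12.9 months". The other, with nivolumab plus chemotherapy in a Chinese subgroup, has 14.3 against 10.2 months. Both are for CPS ≥ 5.

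**The concern.** A Kaplan-Meier median needs the curve to fall to 0.5 within the observed time. Its upper 95% limit needs the upper confidence band to fall that far too. With 39 patients and 5 to 17 months of potential follow-up, the second condition is hard to meet if median OS is anywhere near the cited figures. A stated secondary result would then be reported with an open upper limit, or as not reached, only because observation stopped.

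The missing cut-off is a problem in its own right. Three places in the document imply three different ends to OS observation, and a cut that is not fixed in advance could be chosen after the data are seen. Section 3.2 also plans to relate proteins and microbiota to OS, and that analysis would have only the deaths seen by the cut.

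**Working it through.** **The plan's own figure.** The only size calculation is for ORR: "Assuming the original ORR is 43%, under the conditions of a type I error of 0.05 and a power of 0.8", with a target of 65% and 20% dropout. With the one-sample normal approximation and one-sided α:

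n = [(1.645·√(0.43·0.57) + 0.842·√(0.65·0.35)) / 0.22]² = 30.5, rounded up to 31; 31/0.8 = 38.75, rounded up to 39.

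This matches section 5.1 ("the study plans to enroll a total of 39 participants"). Nothing in that calculation concerns OS.

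**Potential follow-up.** Count months from the start of August 2024. Entry is between month 0 and month 12, and the end of December 2025 is month 17. Potential follow-up is therefore 17 − 12 = 5 to 17 months, median 11 under even accrual (assumed). The share of patients who can be followed for a given time is:

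- 12 months: (17 − 12)/12 = 5/12, about 16 of 39;
- 14.3 months: (17 − 14.3)/12 = 0.225, about 9 of 39;
- 18.4 months: none.

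If the true median is 18.4 months, any median this cut produces must lie below 17 months, and so below the truth.

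**Expected deaths.** With exponential OS, λ = ln 2 / median and no loss to follow-up:

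D = 39 × [1 − (e^(−5λ) − e^(−17λ)) / (12λ)].

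For 14.3 months, λ = 0.0485 and D = 39 × [1 − (0.785 − 0.439)/0.582] = 15.8. The other medians are done in the same way. For a cut at the end of July 2026 (month 24), 5 and 17 become 12 and 24.

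**Estimability.** This was simulated with 39 patients, uniform entry over 12 months, exponential OS and administrative censoring at the cut (3,000 to 6,000 trials per setting). The median counts as reached if the Kaplan-Meier curve falls to 0.5 or below. The upper limit counts as finite if the pointwise upper 95% band does so; the ranges span log-log and linear bands.

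| True median OS (months) | Deaths, Dec 2025 | Median reached | Upper limit finite | Deaths, Jul 2026 | Median reached | Upper limit finite |
|---|---|---|---|---|---|---|
| 10.2 | 20.0 | 91% | 28–32% | 27.2 | 99.8% | 87–88% |
| 12.9 | 17.0 | 72% | 8–13% | 23.9 | 98% | 53–56% |
| 14.3 | 15.8 | 60% | 4–7% | 22.5 | 94% | 37–40% |
| 18.4 | 13.0 | 33% | 1–3% | 19.0 | 74% | 10–13% |

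**Sensitivity at December 2025**, same order of medians:

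- 20% lost by 12 months: median reached in 88% / 69% / 59% / 34%; upper limit in 23–30% / 5–11% / 4–8% / 0–3%.
- Weibull shape 1.3: median reached in 96% / 76% / 63% / 32%; upper limit in 41–48% / 12–17% / 5–9% / 1–3%.
- Medians outside the cited range (assumed): at 8 months, median reached in 99% and upper limit in 64–67%; at 24 months, 16% and 0–1%.

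**PFS, same cut.** At the cited 7.7 / 8.3 months the median is reached in 99% / 98% of trials and the upper limit in about 67–71% / 58–61%. PFS is much less affected.

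**Visits against the schedule.** Section 6 asks for 3-monthly follow-up after six cycles in patients without progression. Six cycles take 6 × 21 = 126 days. A patient entered at the end of July 2025 finishes in early December 2025, and the first such visit falls around March 2026, after section 13's follow-up line has ended. Section 6 gives no schedule for survival contact after progression.

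**The case against.** Section 13 is a three-line work plan and does not say that survival follow-up stops in December 2025. Sections 6 and the synopsis point to longer observation. A reader might infer that follow-up definitely closes in December 2025; the documents support this only as one reading. The objection stands, and the firm defect is the missing cut-off.

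A reader might also infer that median OS cannot be delivered at all. The figures do not support that. At true medians of 10.2 to 14.3 months the point estimate is reached in 60–91% of trials. What is usually missing is the upper limit, and a median with an open upper limit, or one reported as not reached, is a valid result.

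The benchmarks may not apply. They come from CPS ≥ 5 populations and are not specific to liver metastasis. This trial has no CPS criterion and admits ECOG 0–2, and section 1 describes long-term survival with liver metastasis as very poor. Shorter survival would ease the problem, as the 8-month case shows. Adding ramucirumab could work the other way. The direction is unknown, so the result has to be read as a range.

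Finally, a later cut does not cure the problem. At July 2026 the upper limit is still finite in only about 37–40% of trials at 14.3 months and about 9–13% at 18.4. This also stands, and it is why the fix does not rely on the later date alone.

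**Conclusion.** The point holds in this form: the plan states no OS cut-off, and its three indications of when OS observation ends do not agree. If December 2025 is the cut, a complete 95% CI for median OS is obtained in a minority of trials at every OS median the document cites: at most about one third under exponential survival, and under half in the Weibull check. The median itself is more likely missed than reached only near 18.4 months, the cited figure for sintilimab plus chemotherapy.

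This rests on even accrual of 39 patients and on OS medians taken from CPS ≥ 5 populations, because the document gives none for liver metastasis. At an assumed 8 months both the median and its upper limit would usually be obtained. OS is a secondary endpoint, so the primary ORR analysis and its sample size are not affected. The change is worth making but is not critical.

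**What to change.** 1. State one OS data cut-off and make section 6, section 13 and the synopsis agree with it. The end of July 2026 is the natural date: it is the synopsis end date and gives every patient 12 months of potential follow-up. The ORR analysis can keep its current date.
2. In section 13, continue vital-status follow-up to that cut. In section 6, add survival contact for patients who have progressed.
3. In section 11 and the synopsis, add the 12-month OS rate and the 6-month PFS rate (Kaplan-Meier, 95% CI) beside the medians. Report a median or limit as not reached where that applies, and give median follow-up by reverse Kaplan-Meier.

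Moving the cut from December 2025 to July 2026 raises the chance of reaching the median from about 60% to 94–95% at a true 14.3 months, and from 33% to 74% at 18.4. The 95% CI for the 12-month rate narrows from a width of about 0.36 to about 0.31. That gain is modest, but the 12-month rate can be estimated whether or not the median is reached.

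The cost is a telephone or record check of vital status and some wording. OS would be reported later than ORR, and OS analysis and writing would have to move past the June 2026 end in section 13, and so past the July 2026 study end in the synopsis.
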